## Listing:

Demographic characteristics and baseline physical measurements will be displayed for enrolled population. Baseline variables such as tumor tissue collection details (biopsy site, location of biopsy, lymph node location), and tumor markers (type of tumor marker, result) will be listed.

## 7.3.3 Medical History

Summary:

Medical history will be summarized by the incidence of subjects in safety population with reported Medical Dictionary for Regulatory Activities (MedDRA® Version 18.0) by system organ class (SOC) and preferred terms (PTs).

Listing:

Medical history will be listed for enrolled population.

### 7.4 Extent of Exposure

The extent of exposure will be characterized according to the number of subjects exposed, the duration of exposure, and the dose to which they were exposed.

### 7.4.1 Study Therapy

Summary:

Descriptive statistics will be provided by treatment for the following:

- Exposure to cabiralizumab (weeks)
- Exposure to nivolumab (weeks)

Exposure (weeks) is defined as the (number of days between start date of first injection and stop date of last injection + 21)/ 7 for Cohort 1aD1, and (number of days between start date of first injection and stop date of last injection + 14)/ 7 for all the other cohorts.

- Total cabiralizumab dose administered (mg and mg/kg)
- Total nivolumab dose administered (mg and mg/kg)
- Number of cabiralizumab doses administered
- Number of nivolumab doses administered
- Relative Dose Intensity of cabiralizumab and nivolumab

Relative dose intensity is defined as ([total dose administered in mg/kg]/ [planned total b dose])\*100, where planned total dose is the prescribed starting dose in mg/kg times the exposure to study drug divided by 14 and 21 for all the cohorts except for 1aD1 and cohort 1aD1, respectively.

In addition, number and percentage will be provided for the subjects with relative dose intensity <50, 50-<70, 70-<90, 90-<110 and >=110.

Listing:

- Study drug administration details will be presented in a listing.
- Calculated exposure parameters for all the subjects

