### 6 STUDY PERIODS, TREATMENT REGIMENS

### 6.1 Study Periods

The study will consist of 3 periods including screening (up to 28 days), treatment, and follow-up. **Screening:** Subjects who have fully consented to participation in the study will undergo screening assessments within 28 days (4 weeks) prior to administration of the first infusion of study treatment.

**Treatment cycles**: (including end of the DLT period and Phase-1a extended treatment period.) For subjects in the monotherapy cohorts: cabiralizumab infusion administered as a 30-minute IV infusion on Day 1 of each 14-day treatment cycle.

For the combination therapy: nivolumab administered first as a 30-minute IV infusion, with a 30to 60-minute rest, followed by a 30-minute infusion of cabiralizumab on Day 1 of each 14-day treatment cycle.

For cohort 1aD (Subjects in 3-week dosing regimen cohort): Study drugs on Day 1 of each 21-day treatment cycle.

**End-of-Treatment Follow-up Period:** All subjects should return to the clinic 28 ( $\pm$ 7) days and 100 ( $\pm$ 7) days from their last dose of study drug to complete the End-of-Treatment Follow-up

Period, irrespective of whether a subject is discontinued from the study drug at a planned visit or mid-cycle. Subjects should continue onto Long-Term Follow-up after completing the End-of-Treatment. Subjects will be followed every 12 ( $\pm 2$ ) weeks for survival, or more frequently as needed.

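### The relative dose intensity formula divides an exposure in weeks by a cycle length in days, so a fully compliant patient scores 700% and practically everyone lands in the top class

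*SAP*

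**What the plan says.** Everything needed is in SAP section 7.4.1 (Study Therapy), apart from the cycle lengths.

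- **Exposure, cohort 1aD1:** "Exposure (weeks) is defined as the (number of days between start date of first injection and stop date of last injection + 21)/ 7".
- **Exposure, all other cohorts:** "number of days between start date of first injection and stop date of last injection + 14)/ 7 for all the other cohorts".
- **Planned total dose:** "planned total dose is the prescribed starting dose in mg/kg times the exposure to study drug divided by 14 and 21", with 14 for every cohort except 1aD1 and 21 for 1aD1.
- **RDI:** total mg/kg given, divided by the planned total dose, times 100.
- **Reporting:** counts and percentages of subjects with "relative dose intensity <50, 50-<70, 70-<90, 90-<110 and >=110".

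SAP section 6.1 shows where the divisors come from. For monotherapy it has "cabiralizumab infusion administered as a 30-minute IV infusion on Day 1 of each 14-day treatment cycle"; the two-week combination cohorts also use 14-day cycles, and cohort 1aD uses 21-day cycles.

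**The concern.** The planned total dose should be the starting dose multiplied by the number of dosing intervals in the exposure period. That count is right only if the exposure and the cycle length are in the same unit. Here the exposure has already been divided by 7 to give weeks, and it is then divided by a cycle length in days. The number of planned doses comes out at one seventh of its proper value.

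Among the exposure summaries in section 7.4.1, RDI is the only one that sets the dose delivered against the dose planned. Protocol section 4.3.4 does not allow dose reductions, so under-delivery during treatment shows itself mainly through delays, missed doses and incomplete infusions. RDI is meant to pick these up. Inflated sevenfold, it no longer separates a patient with substantial under-delivery from one who was fully dosed, and the per-subject listing of calculated exposure parameters carries the same error.

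**Working it through.** The documents give no numerical RDI, so there is no figure of the plan's own to reproduce. The check applies the SAP's formulas as written.

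**Inputs**
- Cycle length *c* = 14 days, or 21 days for 1aD1 (SAP 6.1).
- Exposure in weeks = (days from first to last infusion + *c*)/7 (SAP 7.4.1).
- Planned total dose = *d* × exposure/*c*, where *d* is the starting dose in mg/kg (SAP 7.4.1).
- RDI = 100 × total mg/kg given/planned total dose (SAP 7.4.1).
- Usual longest gap between doses = 6 weeks, or 42 days; longer gaps need Medical Monitor agreement (Protocol 4.3.6).

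**Fully compliant patient: *k* full doses, each *c* days apart**
- Days from first to last infusion = *c*(*k* − 1).
- Exposure = (*c*(*k* − 1) + *c*)/7 = *ck*/7 weeks.
- Planned total dose = *d* × (*ck*/7)/*c* = *dk*/7.
- RDI = 100 × *dk*/(*dk*/7) = **700%**.

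The terms *c*, *d* and *k* cancel, so the result is the same for either schedule, either drug and any number of doses. For example, six doses of 4 mg/kg every 14 days give an exposure of (70 + 14)/7 = 12 weeks. The planned dose is 4 × 12/14 = 3.43 mg/kg against 24 mg/kg given, which is 700%. Counting days inclusively (adding 1) changes this only to between 653% and 699% for 1 to 26 doses.

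**What the class limits then mean.** Each printed limit corresponds to a true RDI one seventh as large.

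| Printed limit | True RDI |
|---|---|
| 50% | 7.1% |
| 70% | 10.0% |
| 90% | 12.9% |
| 110% | 15.7% |

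The class meant for full delivery, 90 to under 110, would hold only patients who received 12.9% to under 15.7% of plan.

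**Severe delay: every dose 42 days apart.** Exposure is (42(*k* − 1) + *c*)/7 weeks.

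| Doses | 14-day cycle, as written | 14-day cycle, corrected | 21-day cycle, as written | 21-day cycle, corrected |
|---|---|---|---|---|
| 2 | 350.0% | 50.0% | 466.7% | 66.7% |
| 6 | 262.5% | 37.5% | 381.8% | 54.5% |
| 26 | 239.5% | 34.2% | 356.9% | 51.0% |

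As the number of doses grows, the written formula tends to 233% and 350%. Even this pattern never leaves the top class. On the 14-day cycle with full doses, printing below 110% needs an average gap of more than (14*k* × 700/110 − 14)/(*k* − 1) days. That is about 164 days for 2 doses, 104 days for 6 doses, and 89 days in the limit.

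**After correction.** With exposure in days and divisors 14 and 21, or in weeks and divisors 2 and 3, the compliant patient scores 100.0% on both schedules. The delayed patients above fall into the two lowest classes.

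**The case against.** The strongest reply is that the intended meaning can be recovered. The RDI sentence does not repeat the word weeks, its divisors are recognisable as cycle lengths in days, and the reporting classes are centred on 100%. A sensible programmer might use days and get the right answer. One who did not would see 700% on the first output and ask why.

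It is also fair to say that RDI is descriptive and is not a named endpoint. Section 7.4.1 separately reports exposure, total dose and number of doses, and section 7.4.2 reports infusion interruptions and modifications. The tolerability evidence rests chiefly on adverse events, dose-limiting toxicities and discontinuations. Even a corrected RDI says nothing about early discontinuation, because exposure ends one cycle after the last dose.

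These points limit the consequence but do not remove the error. The days reading relies on an exposure variable that the SAP never defines, so correct tables could be produced only by departing from the written rule. Two programmers could differ sevenfold, and someone checking against the SAP would reproduce the wrong one. The classes centred on 100% show that the formula is mistaken, not that it is right. Nor can detection be taken for granted: the SAP's own change history records that version 2.0 amended the cohort label in this calculation, and the unit was left as it was.

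**Conclusion.** The formula is wrong as written. It overstates RDI by a factor of 7 for every treated patient, both drugs and both schedules: 700% for full on-time dosing, and 350% where half the planned dose was delivered. Practically every patient falls in the class of 110% and above. The exceptions are rare, such as a lone infusion stopped with under 15.7% of the dose given, or gaps of several months.

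The conclusion assumes that exposure in the RDI formula is the exposure the SAP defines, in weeks. The exact 700% further assumes full doses at the starting mg/kg and a simple date difference for days. The damage is limited to the RDI summary, its class table and the listing of calculated exposure parameters. Response, survival, dose-limiting toxicity and sample size are untouched.

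**What to change.** In SAP section 7.4.1, define the planned total dose as the starting dose in mg/kg multiplied by exposure in weeks, divided by 2 for all cohorts except 1aD1 and by 3 for 1aD1. Equivalently, define exposure in days (the same expression before division by 7) and keep the divisors 14 and 21. State the unit of exposure in the RDI sentence itself, whichever form is used.

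A simple programming check is that a test patient with every dose given in full and on schedule returns exactly 100% on each schedule.

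The cost is one line of SAP wording and one line of code. No new data are needed and no clinical rule changes. It should be done before the exposure tables are produced.

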#### 7.4.2 Modification of Study Therapy

#### Summary:

The following will be summarized for safety population:

- Number (%) of subjects with at least one infusion interruption
- Number of infusion interruptions per subject
- Number (%) of subjects with at least one infusion modification
- Number of infusion modification per subject

The infusion interruption and modification will be summarized separately for cabiralizumab and nivolumab.

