#### 4.3.2 Dose Delay for Cabiralizumab and Nivolumab

Administration of cabiralizumab and/or nivolumab in combination therapy should be delayed for the following:

- Any Grade 3 fatigue which does not resolve to Grade 1 or baseline before the next treatment visit
- Any drug-related laboratory abnormalities would not require a dose delay unless clinically indicated or specified in the protocol or abnormal laboratory management table (Appendix H). Please discuss with the Sponsor's Medical Monitor or designee as needed.

[REDACTED]

Patients who require a dose delay of cabiralizumab or cabiralizumab /nivolumab should be re-evaluated weekly or more frequently if clinically indicated and resume study drug dosing when re-treatment criteria are met.

If a patient experiences an infusion reaction to cabiralizumab, or nivolumab, or both study drugs, the infusion reaction should be treated following the infusion reaction treatment guidelines [REDACTED]

If the causality of the AE requiring a dose delay is confirmed to be due to one of the study drugs of the combination therapy, the non-offending drug may be continued per protocol taking into account the safety and clinical benefit to the patient.

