#### **4.3.6 Infusion Delays and Missed Doses with Cabiralizumab and Nivolumab**

In case an infusion cannot be administered at a scheduled visit, it must be administered as soon as possible. If the delay is between 1 and 7 days, the procedures at the original scheduled visit should be performed. If the delay is more than 7 days, the infusion at the original scheduled visit will be considered a missed dose and the procedures at the next visit should be performed. If the delay is longer than 7 days, subsequent visits will follow a 2-week (or 3-week in Phase 1a 3-week dosing regimen cohort) dosing interval. If the delay is less than 7 days, the original dosing schedule should be followed. The time between two treatment cycles should be no less than 12 days.

Patients may miss up to up to 6 weeks between doses and may resume the study drug if the event returns to baseline or  $\leq$  Grade 1 within 6 weeks of treatment interruption. Omission of additional dosing longer than 6 weeks for AEs will necessitate the patient’s discontinuation from the study unless allowed by the Sponsor’s Medical Monitor or designee. Patients may miss doses in the

course of participation in the study, including missed doses for scheduled vacations or other personal reasons as needed, but not more than 6 weeks unless approved by the Sponsor's Medical Monitor or designee.

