### 7.4.3 Safety Analyses

Safety analyses will be performed for patients included in the safety population. Incidence of AEs, clinical laboratory information, vital signs, ECOG performance status, weight, and ECGs will be tabulated and summarized.

Incidence of AEs will be summarized overall and with separate summaries for SAEs, AEs leading to discontinuation, AEs leading to death, and NCI-CTCAE v 4.03 Grade 3 or higher AEs.

Weight and vital signs will be summarized descriptively (n, mean, standard deviation, median, minimum, and maximum). ECOG performance status will be summarized categorically and descriptively.

Shift tables displaying patient counts and percentages classified by baseline grade and maximum grade on treatment will be provided for laboratory data by cohort and overall. A marked laboratory change is defined as a shift from a baseline Grade 0 to Grade 3 (non-hematologic) or

Grade 4 (hematologic) on treatment, or a shift from a baseline Grade 1 to Grade 4 on treatment. The number and percentage of patients with marked laboratory changes will be tabulated by cohort and overall.

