#### Phase 1b

• Efficacy

ORR is defined as the total number of subjects with confirmed responses of either complete response (CR) or partial response (PR) divided by the total number of subjects in the response-evaluable population (as defined in section 7.2) per Response Evaluation Criteria in Solid Tumors, version 1.1 (RECIST v1.1) by investigator assessment

• Safety

- The incidence of adverse events (AEs), serious adverse events (SAEs), clinical laboratory abnormalities, and ECG abnormalities
- The incidence of treatment discontinuations, modifications, and interruptions due to adverse events
- Grade 3 and Grade 4 AEs and clinical laboratory abnormalities

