#### 7.6.3 Adverse Events Leading to Discontinuation of Study Therapy

AEs leading to study treatment discontinuation are AEs with action taken = "Drug permanently discontinued". Overall summary of AEs leading to discontinuation and treatment-related AEs leading to discontinuation by worst CTC grade will be presented by SOC/PT. By-subject AEs leading to discontinuation listing will be provided.

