#### 7.6.5.1 Incidence of select AEs

Overall summary of any select AEs, treatment-related select AEs, serious select AEs, treatmentrelated serious select AEs, select AEs leading to discontinuation, treatment-related select AEs leading to discontinuation, by worst CTC grade will be presented by category or subcategory/PT. By-subject select AE listing will also be provided.

The following analyses will be conducted:

- Summary of any select AEs by worst CTC grade (grade 1, 2, 3, 4, 3-4, 5) presented by category or subcategory/PT
- Summary of treatment-related select AEs by worst CTC grade (grade 1, 2, 3, 4, 3-4, 5) presented by category or subcategory/PT
- Summary of any serious select AEs by worst CTC grade (Grade 1, 2, 3, 4, 3-4, 5) presented by category or subcategory/PT
- Summary of treatment-related serious select AEs by worst CTC grade (Grade 1, 2, 3, 4, 3-4, 5) presented by category or subcategory/PT
- Summary of any select AEs leading to discontinuation by worst CTC grade (grade 1, 2, 3, 4, 3-4, 5) presented by category or subcategory/PT
- Summary of treatment-related select AEs leading to discontinuation by worst CTC grade (grade 1, 2, 3, 4, 3-4, 5) presented by category or subcategory/PT

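### AE-caused modifications and interruptions belong to a Phase 1b primary safety endpoint, but the readable SAP specifies an AE-linked summary only for discontinuation

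*SAP*

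**What the plan says.** **Endpoint.** SAP 4.1 (Phase 1b, Safety) lists "The incidence of treatment discontinuations, modifications, and interruptions due to adverse events" among the primary endpoints. Protocol 7.3.2.1 has the same wording. The AE qualifier governs all three components.

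**Discontinuation.** SAP 7.6.3 gives an operational rule: "AEs leading to study treatment discontinuation are AEs with action taken" recorded as permanent discontinuation of the drug. These AEs are tabulated by SOC/PT and worst CTC grade, for all and for treatment-related events, pooling discontinuation of either drug. SAP 7.6.5.1 does the same for select AEs, for example "Summary of any select AEs leading to discontinuation by worst CTC grade".

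**Modification and interruption.** The readable summaries of these are in SAP 7.4.2, under Extent of Exposure. They give, for the safety population and separately for each drug, the "Number (%) of subjects with at least one infusion modification", the matching row for infusion interruption, and the number of each per subject. The section states no cause and does not say what either term includes.

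**Protocol analysis section.** Protocol 7.4.3 plans "separate summaries for SAEs, AEs leading to discontinuation, AEs leading to death" and Grade 3 or higher AEs. It names no summary of AEs leading to interruption, delay or modification.

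**Dosing rules.** Protocol 4.3.2 requires a delay for "Any Grade 3 fatigue which does not resolve to Grade 1 or baseline before the next treatment visit". Protocol 4.3.6 adds: "If the delay is more than 7 days, the infusion at the original scheduled visit will be considered a missed dose". The same section lets dosing resume once the event is back to baseline or no worse than "Grade 1 within 6 weeks of treatment interruption", so there the word interruption means a gap between doses.

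**The concern.** A primary endpoint should have a table that reports it as defined. Here two of its three components have only a count without regard to cause, placed in the exposure section.

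The difference is more than a label. The endpoint is stated at the level of treatment, while SAP 7.4.2 is stated at the level of the infusion. A dose delayed or missed because of toxicity is an interruption in the sense of protocol 4.3.6, yet no infusion took place that could be interrupted or modified. Such an event may fall under neither row of 7.4.2.

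Tolerability of the combination at the recommended dose is a primary Phase 1b objective, and dose reductions are not permitted (protocol 4.3.4). Delays and missed doses are therefore a main way in which toxicity short of discontinuation would show in dosing. If they are not tied to AEs, the report would understate how often toxicity disrupted treatment, or would leave readers to work it out from listings.

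**Working it through.** No figure in the plan is at issue and no event rates are assumed. The check sets the endpoint beside every readable summary that could deliver it.

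**Step 1: count the AE summaries in SAP 7.6.2 to 7.6.6.**

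| SAP section | Summaries listed | On discontinuation | On interruption, delay or modification |
|---|---|---|---|
| 7.6.2 SAEs | 2 | 0 | 0 |
| 7.6.3 Discontinuation | 2 | 2 | 0 |
| 7.6.4 AEs | 2 | 0 | 0 |
| 7.6.5.1 Select AEs | 6 | 2 | 0 |
| 7.6.6 Other events of special interest | 3 | 0 | 0 |
| Total | 2 + 2 + 2 + 6 + 3 = 15 | 2 + 2 = 4 | 0 |

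**Step 2: match the components to the tables.**

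- Discontinuation due to an AE: delivered by 7.6.3, with the select-AE version in 7.6.5.1.
- Modification due to an AE: no AE-linked summary; a count without cause in 7.4.2.
- Interruption due to an AE: no AE-linked summary; a count without cause in 7.4.2.

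One of three components is delivered as the endpoint is worded.

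**Step 3: look for coverage elsewhere.** SAP 7.4.1 summarizes the number of doses given and relative dose intensity, with bands, by drug. Delays and missed doses affect these figures, but their cause does not appear. SAP 7.4.1 and 7.6.4 also provide listings of drug administration and of AEs. A listing is not an incidence. Protocol 7.4.3 adds nothing on interruption or modification.

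**Step 4: compare the terms.** Protocol 4.3.1 names interruption, delay and discontinuation as separate actions. Protocol 4.3.6 uses interruption for a gap between doses. Protocol 4.3.1.2 says cabiralizumab dosing may change because of toxicity and points, among others, to 4.3.2 (delay) and 4.3.10 (infusion reactions). Protocol 4.3.10 prescribes rate cuts and infusion stops. SAP 7.4.2 does not say which of these actions belongs to which row. Two programmers could reasonably build different tables from the same data.

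**Step 5: direction of error.** If 7.4.2 were read as the endpoint, its counts would be too low where AE-driven delays and missed doses fall under neither term, and too high where changes with another cause are counted. The documents give no rates for either, so the net effect cannot be computed.

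**The case against.** Several points can fairly be made for the plan.

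- **The analyses are descriptive and nothing turns on these counts.** This is true: protocol Section 7 says so, and no decision rule uses them. It limits the consequence but does not remove the mismatch, because a descriptive primary endpoint still needs a table that matches its definition.
- **The data are in the listings, and relative dose intensity reflects lost doses.** Also true. The table is unspecified, not impossible. Neither source gives the incidence of AE-caused events.
- **The 7.4.2 counts may be largely AE-driven already.** The readable infusion stops and rate cuts in protocol 4.3.10 all respond to infusion reactions, which are AEs. This has weight, and it makes possible omission of delays the more important worry.
- **The missing definitions may exist in text that cannot be read.** SAP 7.4.3 is absent, parts of protocol 4.3.2, 4.3.3 and 4.3.5 and Appendices F to H are redacted, and protocol 4.3.5 mentions a treatment modification table that is not in the readable text. This stands as a limit on the point.

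A reader might infer that 7.4.2 is inflated by doses missed for vacation, by recalculation for weight change over 10%, or by the study-wide move to a 60-minute nivolumab infusion. The documents do not support that. A missed dose is not plainly an infusion interruption, nothing shows that a weight recalculation would be recorded as an infusion modification, and the 60-minute rule is conditional and would then be the planned rate for later patients. Nor do the documents show that modification is undefined for the study as a whole; only that SAP 7.4.2 does not define it.

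**Conclusion.** The point holds for the readable text. The SAP specifies AE-linked reporting for 1 of the 3 components of this Phase 1b primary safety endpoint: 4 of 15 AE summaries concern discontinuation and 0 concern interruption, delay or modification. SAP 7.4.2 does not fill the gap, because it has no AE restriction and its infusion-level wording may exclude AE-driven delays and missed doses.

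This should be corrected before database lock. It puts no inferential result at risk, and its numerical effect cannot be estimated. The conclusion assumes that the unreadable SAP 7.4.3 holds no such table. The document history suggests that section may concern concomitant medication, but this is an inference. Sections 7.6.2 to 7.6.6, where such a table would belong, are readable in sequence and contain none.

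**What to change.** 1. After SAP 7.6.3, add one table in the same format: safety population, SOC/PT, worst CTC grade, either drug pooled. It should cover AEs whose action taken was dose delay or omission, infusion interruption, or other treatment modification, using the categories that the CRF field provides.
2. Label SAP 7.4.2 as an any-cause exposure table, so that it is not read as the endpoint.
3. State in the SAP which protocol actions, including delays and missed doses, count as interruption and which as modification. Use the protocol's own terms, and check them against its treatment modification table.

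**Cost.** One extra descriptive table, a short definition paragraph and a CRF check. The action-taken field already exists (SAP 7.6.3), and protocol 6.4 already requires capture of laboratory abnormalities that lead to interruption. The only field value shown in the documents is permanent discontinuation. If the CRF does not separate delay, interruption and rate change, the table should use the categories it does have and say so. Pooling the two drugs matches what the SAP does for discontinuation and keeps the request to one table.
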